Participants will not be reimbursed for their time spent in the study, but all participants will be given the option of keeping the Muse-S™ Headband system for continued use post study participation.

Consent and Screening:

Study coordinator will meet with the potential participant who has expressed an interest in participating in the study. They will begin by introducing the study details, and after determining that the subject has continued interest in study participation, will move on to the study consent. If the subject chooses to consent, they will screen the participant for study entry inclusion/exclusion criteria. If the study entry criteria are met, the subject will begin their study participation. They will be asked to complete the study questionnaires.

Please note: Participants must have access to an iOS or Android capable device to take part in this study in order to interact with the Muse-S™ Headband system.

Treatment phase:

During the first three months of study, participants will be asked to complete the intervention portion of the study using the Muse-S™ headband. If the MUSE device is not being used at least 3x a week for 10 minutes a day, the participant may get a reminder email or a phone call to remind them to use the Muse-S™ headband

system. Participants will receive an email link at 90 days from REDCap to complete their questionnaires for the study. If not completed in a timely manner there will be reminders by email and/or phone to complete.

Study Follow-Up Visit:

The study will consist of follow up at 3 month and 6 months.

3 month (questionnaire only visit): questionnaires will be sent via email **NOTE:** once questionnaires are complete the study coordinator will check the PHQ 9 score the same day the participant completes the questionnaire via the electronic link. The coordinator will immediately notify the investigators if the score is severe or subject indicates suicidal ideation. The investigators will contact the patient immediately (same day) and if there is concern for active suicidal thoughts, they will recommend the patient pursue emergency evaluation (such as local ED or 988 suicide prevention hotline) or contact local authorities for a welfare check if the patient declines. If severely depressed but no active thoughts of self-harm/plan, we will recommend an appointment with their PCP, EAP (if Mayo Employee) and offer the resource Psychology Today to help find a mental health provider.

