6-month (on-site visit /phone visit): Consists of a study coordinator visit at Menopause and Women's Sexual Health Center for a final weight, body mass index, blood pressure check and questionnaires for local participants. Participants that are not local or cannot make an on-site visit, questionnaires will be sent by email to be completed and a phone visit will be scheduled with study coordinator. **NOTE:** The PHQ 9 questionnaire will be reviewed at the time of the visit. If the score is severe (20-27) or the subject indicates suicidal ideation the investigators ([name] and [name]) will be notified and will discuss with the patient. If concern for active suicidal thoughts, the investigator will initiate immediate emergency evaluation. If severely depressed but no active thoughts of self-harm/plan, we will recommend an appointment with their PCP, EAP (if Mayo Employee) and offer the resource Psychology Today to help find a mental health provider.

Subject Information

Target accrual: 50 women

Subject population (adults):

This will be an open label single-arm clinical trial that will recruit **50 peri- and postmenopausal women** from the Menopause and Women's Sexual Health Clinic (MWSHC), Community Internal Medicine, Executive Health, or Family Medicine at Mayo Clinic, Rochester, who are identified as having significant sleep disturbance based on a standard questionnaire used for assessment of sleep quality and duration- the Pittsburgh Sleep Quality Index (PSQI). The PSQI is a 19-item questionnaire making up 7 clinically derived component scores. Each of the 7 clinically derived components is given a score from 0-3 to obtain a total score ranging from 0-21. Higher scores indicate worse sleep quality, with a **PSQI score >5 indicating poor sleep quality**.

Inclusion Criteria:

- Women between the ages of **45-65 years** (women in the menopause transition or in menopause, based on clinical assessment)
- **PSQI score >5**, with overall sleep quality rating of "fairly bad" or "very bad".

- Motivation VAS score equal to or greater than 5 with overall motivation rating of on a scale of 0-10 with 0 being not motivated at all and 10 being extremely motivated
- Access to an iPad, iPhone, or android device
- Have ability to provide informed consent

Exclusion Criteria:

- Suspected or untreated obstructive sleep apnea

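### PHQ-9 forms emailed to remote women at 6 months have no same-day check, so a form showing suicidal ideation could go unread until the phone visit

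*Combined protocol and SAP*

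**What the plan says.** Both rules are in the combined protocol and SAP, under Study Follow-Up Visit.

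**6 months.** Local women attend on site and complete the questionnaires as part of that visit. For women who are not local or cannot attend, "questionnaires will be sent by email to be completed and a phone visit will be scheduled with study coordinator". One note then covers both routes: "The PHQ 9 questionnaire will be reviewed at the time of the visit". If the score is 20-27 or suicidal ideation is indicated, the investigators "will be notified and will discuss with the patient". If active suicidal thoughts are a concern, "the investigator will initiate immediate emergency evaluation".

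**3 months.** This contact has no visit: "3 month (questionnaire only visit): questionnaires will be sent via email". Here "the study coordinator will check the PHQ 9 score the same day the participant completes the questionnaire via the electronic link". Then: "The coordinator will immediately notify the investigators if the score is severe or subject indicates suicidal ideation". The investigators must reach the participant that same day.

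**The concern.** The remote 6-month PHQ-9 arrives as the 3-month one does, by email and completed with no staff present. At 3 months the clock starts when the participant completes the form. At 6 months it starts at the visit. On site this makes no difference, because form and visit coincide. On the remote route they need not coincide, and nothing in the text makes them.

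At stake is the safety of remote participants. A woman could report suicidal ideation on a study form and nobody would be required to read it until her scheduled call. The efficacy and feasibility analyses are not touched.

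**Working it through.** There is no figure in the plan to reproduce. The check is a comparison of the two rules, followed by a search for any other text that closes the gap.

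**Step 1. The rules side by side**

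| Step | 3 months, emailed | 6 months, remote |
|---|---|---|
| Delivery | Email | Email, plus a scheduled phone visit |
| PHQ-9 read | Day of completion | At the visit |
| Investigators notified | Immediately | Notified, no time given |
| Investigator speaks to participant | Same day | Discussion, no time given |
| Active suicidal thoughts | Emergency evaluation recommended (local ED or 988); welfare check if she declines | Investigator starts emergency evaluation immediately |

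The last 6-month step is firmer than its 3-month counterpart. It cannot begin, however, until someone has read the form.

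**Step 2. Does other text close the gap?**

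- The same-day check is written inside the 3-month paragraph. The 6-month paragraph has its own note with a different rule, so the 3-month rule does not carry over.
- Methods says that data go into REDCap at baseline, 3 months and 6 months. No automatic PHQ-9 alert is described.
- Treatment phase provides reminders for late questionnaires, which concerns completion and not review.
- No other section sets a window or an order for the remote form and the call.

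**Step 3. Cases for the remote form**

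Let d be the number of days from completing the form to the call.

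- Completed during the call or on that day: d = 0, no delay.
- Completed on an earlier day: delay to review = d. As an assumed illustration, d = 1, 3 or 7 gives 1, 3 or 7 days.
- Completed after the call: the visit is over, and the note gives no time for reading the form.

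For the emailed 3-month form, the delay to review is 0 days by rule.

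**Step 4. How many women?**

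Flagged forms read late = R × f × p, where

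- R = women on the remote route: 0 to 50, from the target accrual of 50;
- f = proportion of forms flagged: not given;
- p = proportion of forms completed on a day before the call: not given, 0 to 1.

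With p = 0 the result is R × f × 0 = 0. Since R, f and p are all unknown, no expected number or probability is reported.

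**The case against.** The strongest reply is that the delay is only one reading. The protocol pairs the emailed form with a scheduled phone visit in one sentence and applies a single review rule to both routes, so the form may be meant as part of the call. Staff send the email and book the call, and can align the two. The contacts also differ in kind: at 3 months nobody speaks to the participant, so a same-day check is the only safeguard, whereas at 6 months a live conversation is planned. The 6-month emergency step is immediate, and women with a known, active, untreated, clinically significant psychiatric condition are excluded. Neither a delay nor an affected participant can be shown from the documents.

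Much of this is fair. The documents do not show that a delay will happen, and tying review to a scheduled contact is an understandable choice. Urgency is also not absent from the 6-month note, although it appears only at the last step.

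Three points remain. Aligning form and call is possible but not required. The phone visit protects the participant only once it takes place. The exclusion covers known conditions at entry, while the protocol itself provides escalation at both follow-ups and so treats these events as possible.

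It can also be said that completing the form during the call would be a simpler remedy. It would work if enforced, but it would not cover a woman who opens the emailed form early or whose call is postponed. A rule triggered by completion covers both.

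**Conclusion.** The concern holds. For remote 6-month participants, the protocol permits a gap of unstated length between a form reporting severe depression or suicidal ideation and anyone reading it, and sets no time for the investigators' first contact after that. For the same questionnaire emailed at 3 months, the permitted gap is 0 days.

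Confidence is high that the interval is missing. Nothing is claimed about how often a delay would occur: the number affected may be zero and cannot be estimated from the documents. On-site participants and the analysis are unaffected. The point rates as should-fix because one unread report could be serious and the remedy is small.

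**What to change.** Add to the 6-month note, in words such as these:

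> When a participant completes the 6-month questionnaires remotely, the coordinator reads the PHQ-9 on the day of completion and alerts the investigators at once if the score is 20-27 or suicidal ideation is reported. An investigator speaks to the participant that day.

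Keep the existing 6-month requirement that the investigator initiates emergency evaluation immediately. Add the 3-month remote steps (local ED or 988, and a welfare check if she declines) as a supplement. They should not replace the 6-month step, because the 3-month text only recommends evaluation.

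The cost is one or two sentences of protocol wording, plus a little coordinator and investigator time on days when remote 6-month forms arrive. The same check already runs at 3 months.

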MUSE Device to Improve Sleep Quality in Midlife Women

NCT05972486

31January2024

IRB Minimal Risk Protocol Template

General Study Information

Principal Investigator: [name], PA-C

Co- Principal Investigator: [name], DNP

Co- Investigator: [name]

Lead Coordinator: [name]

Study Title: MUSE Device to Improve Sleep Quality in Midlife Women

Protocol version number and date: V4 01/31/2024

Research Question and Aims

Hypothesis:

We hypothesize that the daily use of the Muse-S headband system will be an effective strategy for improving the sleep quality in peri- and postmenopausal women. We anticipate that the women who utilize the Muse-S headband will have improvements in time to sleep onset and sleep maintenance. We also anticipate a positive correlation between duration and frequency of use of the device and the improvement in sleep quality.

Aims, purpose, or objectives:

1. To obtain preliminary evidence regarding the feasibility of using the Muse-S headband system for management of sleep disturbances in peri- and postmenopausal women.
2. To obtain preliminary data on the effectiveness of the Muse-S headband system for management of sleep disturbances in peri- and postmenopausal women and to ascertain whether duration of treatment impacts efficacy.
3. To obtain preliminary data on the effectiveness of the Muse-S headband system in improving secondary outcomes of sleep quality including stress levels, mood and sexual function.

The overarching purpose of this study is to obtain preliminary evidence regarding the efficacy of the Muse-S headband system for management of sleep disturbances (insomnia and sleep disruption) in midlife women. This goal will be achieved with the following specific aims:

Objectives: The overarching goal of this project is to test the feasibility and efficacy of the Muse-S™ Headband, an electroencephalographic device, in management of sleep disturbances in midlife women.

Background:

Sleep problems (insomnia and sleep disruption) affect nearly half the women during the menopause transition and the postmenopausal years. The etiology of sleep disturbances in peri- and postmenopausal women is

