- Moderate to severe vasomotor symptoms warranting prescription medication use. The FDA categories for hot flash severity are classified as mild (sensation of heat without sweating), moderate (sensation of heat with sweating, able to continue activity), or severe (sensation of heat with sweating cause cessation of activity).
- Use of hormone therapy or hypnotic agents
- Use of supplements known to affect sleep
- A known, active, untreated clinically significant psychiatric condition
- Use of an investigational drug within 30 days of study enrollment or presence of a known history of any condition or factor judged by the investigator to preclude participation in the study or which might hinder adherence.
- Currently (within the past 3 weeks) been practicing mindfulness training on a weekly/regular basis

Potentially eligible participants will be identified from the MWSHC, Community Internal Medicine, Executive Health, or Family Medicine, where midlife women are evaluated for menopause and sexual health-related concerns. All the women seen in these areas will complete multiple questionnaires as part of their clinical evaluation, including the PSQI. They also complete questionnaires assessing mood (Patient Health Questionnaire 9, PHQ-9), anxiety (Generalized Anxiety Disorder 7, GAD-7), and sexual function (Female Sexual Function Index, FSFI and the Female Sexual Distress Score-Revised, FSDS-R), Quality of Life-LASA), Perceived Stress Scale (PSS) and Resilience- (CD-RS10).

Review of medical records, images, specimens

- The study involves data that exist at the time of IRB submission and data that will be generated after IRB submission. Include this activity in the Methods section.

Data Analysis**Data Analysis Plan:**

Demographic characteristics are described using mean and standard deviations or frequencies and percentages based on the type of variable. For the primary aims being the feasibility and efficacy of the MUSE device, descriptive statistics and graphical displays will be presented for data obtained on frequency and duration of use over the treatment time of six months. A linear mixed model with repeated measures for each time point that

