stress and sleep were taken. That information will be utilized to estimate the association between the average of time spent using the Muse-S with the stress and sleep level outcome. As secondary aim, the results of questionnaires for stress levels, mood and sexual function will be analyzed using the same linear mixed model with questionnaires being done at different intervals of the study to determine changes over time. Given the number of outcomes assessed, all analyses will be considered exploratory.

Endpoints:Primary Hypothesis:

- The regular use of the Muse headband will increase quality and quantity of sleep.

Secondary Hypothesis:

- The regular use of the Muse headband will decrease perceived stress levels, decrease anxiety, and improve sexual health.

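### The planned association between Muse-S use and outcome is open to confounding by motivation, which is scored at entry but not in the model

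*Combined protocol and SAP*

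**What the plan says.** All references are to the combined protocol and SAP.

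- **Inclusion Criteria:** entry requires a "Motivation VAS score equal to or greater than 5", rated from 0 (not motivated at all) to 10. The score is not among the study questionnaires listed under Methods, and the Data Analysis Plan does not mention it.
- **Exclusion Criteria:** a further rule removes women with any condition or factor "judged by the investigator to preclude participation in the study or which might hinder adherence".
- **Hypothesis:** "We also anticipate a positive correlation between duration and frequency of use of the device and the improvement in sleep quality".
- **Data Analysis Plan:** a linear mixed model with repeated measures is to "estimate the association between the average of time spent using the Muse-S with the stress and sleep level outcome". No covariate is named: not motivation, age or baseline severity. For feasibility, "descriptive statistics and graphical displays will be presented for data obtained on frequency and duration of use" over six months. All analyses are declared exploratory, and no significance level is given.
- **Subject Information:** "This will be an open label single-arm clinical trial", and "Target accrual: 50 women".
- **Treatment phase:** "If the MUSE device is not being used at least 3x a week for 10 minutes a day", the participant may be sent a reminder.
- **Methods:** data are recorded at baseline, 3 months and 6 months, and the sleep, stress and mood outcomes are questionnaires.

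**The concern.** The amount of use is decided by each woman, not assigned. A woman who is keener at entry may use the headband more and may also rate her sleep and stress as more improved, knowing what she is receiving. There is no control arm or blinding to separate these routes. A positive association between use and improvement, which the protocol predicts, could then appear even if use did nothing.

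The trial must obtain a direct measure of this confounder before entry, but the plan does not use it. If the score serves only as a pass/fail check and its value is not kept, the adjustment cannot be made later.

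**Working it through.** **1. The plan's own figure.** The only stated figure is the target of 50 women. No alpha, power, effect size or SD is given, so there is no derivation to reproduce. What follows is a sensitivity calculation on assumed correlations. It uses a simple correlation rather than the planned mixed model, and two-sided 0.05, which is also an assumption.

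**2. Spurious correlation with no device effect.** If motivation M is the only link between use U and improvement D, then r(U,D) = r(M,U) × r(M,D). Taking the assumed values to apply among enrolled women:

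- 0.1 × 0.1 = 0.01
- 0.3 × 0.3 = 0.09
- 0.4 × 0.4 = 0.16

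**3. Chance of a positive significant result at n = 50.** By Fisher's z, this is 1 − Φ(1.96 − atanh(r) × √47), with √47 = 6.856. With r = 0 it is 2.5%.

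| Spurious r | atanh(r) × √47 | Positive rejections |
|---|---|---|
| 0.01 | 0.069 | 2.9% |
| 0.09 | 0.619 | 9.0% |
| 0.16 | 1.106 | 19.7% |

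A simulation of 20,000 trials gave 8.8% and 19.7% for the last two rows. In a separate simulation, adding motivation as a linear covariate brought them to 2.6% and 2.3%. For scale, the 95% confidence half-width for a correlation near zero at n = 50 is tanh(1.96/√47) = 0.28.

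**4. Effect of the entry rule.** Suppose instead that the assumed correlations describe unselected women. Requiring a score of at least 5 narrows the spread of motivation. Let k be the ratio of the variance of M after selection to that before. Each correlation ρ becomes ρ√k / √(ρ²k + 1 − ρ²), and the spurious r is its square when both links equal ρ. Taking M as Normal with SD 2 (assumed), k = 0.363 if the mean is 5 (half pass) and 0.773 if the mean is 8 (93% pass).

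- ρ = 0.1: spurious r is 0.004 to 0.008.
- ρ = 0.3, k = 0.363: 0.181/0.971 = 0.186, squared 0.035. With k = 0.773: 0.264/0.990 = 0.266, squared 0.071. Positive rejections are about 4% to 7%.
- ρ = 0.4: by the same steps, 0.254² = 0.065 to 0.358² = 0.128. Positive rejections are about 6% to 14%.

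The entry rule therefore weakens this confounding without removing it.

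**5. Where motivation must enter the model.** The plan does not say whether baseline is one of the repeated outcomes. If it is, the effect of use on improvement is the use-by-time term. With a random intercept and complete visits, that term is estimated from within-woman changes, and anything constant across a woman's visits cancels:

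- y(later) − y(baseline) = time effect + (use × time) × U + error.

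A main effect of motivation cancels in the subtraction and leaves the use-by-time estimate unchanged. A simulation at 0.4 and 0.4 with two visits and no true effect showed this: the bias was the same with and without the main effect, and positive rejections were 18.7% both times. Adding motivation by time removed the bias. If only the 3- and 6-month outcomes are modelled, with the baseline value as a covariate, a motivation main effect does the adjustment.

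**The case against.** The strongest reply is that the documents contain no data linking motivation to use or to improvement, and that the plan claims little: preliminary aims, exploratory analyses and an association. It adds that the model names no covariate, so motivation is only one example of an unspecified model, and that adjusting for it leaves reverse causation (women who feel benefit use the device more) and the low-use reminders untouched.

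Much of this stands. The size is unknown and may be negligible, and the wider gap is the missing model specification. But an exploratory label limits how firmly a result is claimed; it does not remove bias from an estimate that answers a stated hypothesis. Remaining confounders do not justify leaving out one that screening already scores.

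A reader might infer three stronger things that the documents do not support:

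- **That the correlation is confounded.** Nothing in the documents measures either link, so only the opening for confounding is established.
- **That the entry rule creates the problem.** Under the assumptions in step 4 it reduces it.
- **That uptake will be overstated.** The plan describes use among enrolled women, and that description is correct for them. It sets no uptake proportion, threshold or denominator. Overstatement would arise only if the result were carried over to women not selected for motivation. Women must also express interest and consent before the entry criteria are checked, so the sample is self-selected in any case.

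**Conclusion.** The point holds as a gap in the analysis plan: the use–outcome association is open to confounding by motivation, and a score obtained at entry is not used to reduce it. Under no device effect the spurious correlation is about 0.01 if both links are 0.1, and 0.09 or 0.16 if both are 0.3 or 0.4 among enrolled women, with positive rejections of about 3%, 9% and 20% against 2.5%. If 0.3 and 0.4 describe unselected women, the spurious correlation falls to 0.035–0.071 and 0.065–0.128. All of this rests on assumed correlations, linear links, an assumed distribution of scores for the second set, and a simple correlation in place of the mixed model.

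The point does not invalidate the trial or call for changing the entry rule. It is worth acting on because the correction is nearly free and depends on the score being kept.

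**What to change.** 1. State that the entry motivation score is recorded and retained in the study data for every enrolled woman.
2. Specify the use–outcome model: 3- and 6-month outcomes on average use, adjusted for the baseline value of that outcome (PSQI for the PSQI analysis) and for entry motivation. If baseline is kept as one of the repeated outcomes, include motivation by time alongside use by time; a motivation main effect alone is not enough.
3. Describe the result as associational, noting that reverse causation and the low-use reminders remain.
4. As a secondary reporting point, give the number of women excluded for a motivation score below 5, and state that the feasibility findings apply to women scoring at least 5.

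The cost is one or two model terms per outcome, retention of a score already obtained, one screening-log count and a sentence in the report. There is no added visit, questionnaire or participant.

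### The use-response analysis targets the level of sleep rather than its improvement, and leaves the model terms and the use-averaging window undefined

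*Combined protocol and SAP*

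**What the plan says.** The Hypothesis section states: "We also anticipate a positive correlation between duration and frequency of use of the device and the improvement in sleep quality". The primary hypothesis under Endpoints is broader: "The regular use of the Muse headband will increase quality and quantity of sleep".

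The Data Analysis Plan first describes "frequency and duration of use over the treatment time of six months". It then names the model: "A linear mixed model with repeated measures for each time point that" "stress and sleep were taken". That sentence has no main verb and lists no fixed or random effects. The next sentence gives the purpose, which is to "estimate the association between the average of time spent using the Muse-S with the stress and sleep level outcome". The exposure is average time; frequency of use is described but not modelled. No visit-by-use term, change score or baseline adjustment is mentioned, and no window is given for the average.

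The secondary questionnaires are to be "analyzed using the same linear mixed model with questionnaires being done at different intervals of the study to determine changes over time". The section closes: "Given the number of outcomes assessed, all analyses will be considered exploratory".

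Under Methods, questionnaire data are recorded at entry and at months 3 and 6, and the device is handed out at study entry.

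**The concern.** Improvement is a change from baseline; the stated target is a level. The baseline score precedes any use, so an association between later use and that score cannot be a device effect. It reflects which women go on to use the headband more. A model that pools baseline with follow-up and gives use a single coefficient mixes that selection with the response and shrinks the response.

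This is the only analysis offered for the use-response hypothesis. A diluted or contaminated slope could hide a real relation, or show one where none exists, in a study whose purpose is to supply preliminary evidence.

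**Working it through.** **Inputs.** From the documents: three visits (0, 3, 6 months), device issued at entry, 50 women in one arm. The plan gives no SD, within-woman correlation, effect size or test level, so it has no figure of its own to reproduce. Every SD, effect and correlation below is an assumption, and rejection rates use a nominal 5% test.

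**Step 1: one average per woman, no visit-by-use term.** Let b0, b3 and b6 be the slopes of the score on average use at the three visits. With complete data the use coefficient is (b0 + b3 + b6)/3, with or without a visit main effect.

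- No baseline link, constant response b: (0 + b + b)/3 = 2b/3.
- A link g present at every visit, plus response b at follow-up: (g + (g + b) + (g + b))/3 = g + 2b/3.

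Higher PSQI is worse, so benefit is a negative b. With b = −0.9 points per SD of use and g = 0, the coefficient is 2 × (−0.9)/3 = −0.60. Fitted mixed models with a visit effect (within-woman correlation rho 0.5) gave −0.60, against −0.90 for visit-by-use. With 20% dropout they gave −0.54 and −0.90.

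**Step 2: both readings of average use.** Simulation: 300 data sets of 50 women per row, between-woman SD 2.5, within-woman SD 2.0, use with mean 10 and SD 5 min/day. Slopes are PSQI points per min/day, with rejection rates in brackets. All models include visit.

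| g | b | g + 2b/3 | One average, no interaction | Visit-by-use | Use up to each visit, zero at baseline |
|---|---|---|---|---|---|
| 0 | 0 | 0 | 0.009 (6%) | 0.008 (7%) | 0.010 (7%) |
| 0 | −0.15 | −0.10 | −0.096 (23%) | −0.157 (60%) | −0.153 (70%) |
| 0.10 | −0.15 | 0.00 | 0.002 (6%) | −0.152 (55%) | −0.112 (44%) |
| 0.15 | 0 | 0.15 | 0.155 (47%) | 0.002 (7%) | 0.060 (19%) |
| −0.15 | 0 | −0.15 | −0.149 (50%) | 0.000 (6%) | −0.057 (16%) |
| 0.15 | −0.15 | 0.05 | 0.054 (13%) | −0.146 (53%) | −0.088 (30%) |

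The last column shows no dilution when g = 0. It is biased when g is not zero.

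**Step 3: precision with no baseline link.** Take equal within-woman correlation rho, and unit variances of score and use. Squared z per n·b²:

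- Level coefficient: (4/9)/((1 + 2rho)/3) = 4/(3(1 + 2rho)).
- Single-visit change contrast: 1/(2(1 − rho)). It equals the level coefficient when 8(1 − rho) = 3(1 + 2rho), so rho = 5/14 = 0.36.
- Mean follow-up adjusted for baseline: 2/((1 + 2rho)(1 − rho)). Its ratio to the level coefficient is 1.5/(1 − rho), above 1 at every rho.

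Simulated power (20,000 trials per setting, SD 3, effect −0.9 per SD of use) at rho 0.3/0.5/0.72: level 47/39/33%, single-visit change 41/54/77%, baseline-adjusted 76/81/92%.

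**Step 4: no single method is safe under every baseline link.** Take no device effect, SD 3 and a correlation of 0.2 between use and baseline score.

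- *Use follows the stable sleep level.* b0 = b3 = b6 = 0.2 × 3 = 0.60. The level coefficient is 0.60 (rejects 49/41/34% at rho 0.3/0.5/0.72). The change contrast is 0.60 − 0.60 = 0. Baseline adjustment at rho 0.3 leaves 3 × (0.2 − 0.3 × 0.2)/(1 − 0.2²) = 3 × 0.14/0.96 = 0.44.
- *Use follows the observed baseline score*, rho 0.3. b0 = 0.60 and b3 = b6 = 0.3 × 0.60 = 0.18. The level coefficient is (0.60 + 0.18 + 0.18)/3 = 0.32 (rejects 17%). The change contrast is 0.18 − 0.60 = −0.42 (16% with both follow-ups pooled). Baseline adjustment gives 0.

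**Step 5: the window.** If use after month 3 correlates 0.2 or 0.3 with 3-month improvement, relating six-month use to 3-month change gives false signals in 11–12% or 19–23% of trials. Use counted up to the 3-month questionnaire gives 5%.

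**The case against.** The strongest reply is that the plan writes no model formula. The interaction is unstated, not excluded. Average time can also be read as average use up to each questionnaire, which is zero at baseline because the device is only then issued. On that reading the dilution is gone. In a further check with SD 3 and effect −0.9 (300 fits per setting, rho 0.3/0.5/0.72), such a term gave −0.90/−0.91/−0.90 and rejected 82/84/95%, close to baseline adjustment in the same data (78/83/93%). This stands: two-thirds is a conditional result, and a reader who infers that the plan commits to a diluted coefficient goes beyond the text. It does not clear the plan. The text does not choose this reading, and at rho 0.3, with no effect and use tied to the stable sleep level at correlation 0.2, the term still rejected 22% (baseline adjustment 21%).

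Three further replies hold in part. The baseline link is hypothetical: the documents neither state nor exclude one. The reference to the same model and to changes over time implies a visit effect, which gives mean change, so it would be wrong to infer that overall improvement cannot be estimated. And everything is labelled exploratory with no test level, so a reader should not infer a wrong formal decision.

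Nor are change contrasts always superior: Steps 3 and 4 show where they are less precise or biased.

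**Conclusion.** The mismatch is real and worth correcting. The hypothesis concerns use and improvement; the only stated use-response target is average time against the sleep level, over measurements that include a pre-device baseline. That the baseline is included follows from joining the Data Analysis Plan with the Methods schedule.

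With one average per woman and no visit-by-use term, a constant response is reported at two-thirds of its size. That is algebra, given complete data and equal slopes at 3 and 6 months. A link between use and sleep that persists from baseline is added in full, and can cancel or reverse a true response. With use averaged up to each visit the first problem goes and part of the second remains. The plan does not say which applies. The rejection rates depend on assumed SDs, effects and correlations and show direction and order of size only.

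The consequence is a potentially misleading preliminary estimate in an exploratory, single-arm study.

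**What to change.** Replace the target sentence in the Data Analysis Plan with:

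> For each sleep and stress score, a linear mixed model will include categorical visit (0, 3, 6 months), average use (centred) and visit-by-use, with within-woman correlation. The 3- and 6-month visit-by-use contrasts, each with use averaged up to that questionnaire, estimate the association of use with change from baseline, with 95% CI. Follow-up score on use adjusted for baseline score will also be reported, and both will be repeated with sessions per week. Use is self-selected, so results are observational and exploratory.

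The two windows mean fitting the model twice, once per averaging period. Centring matters because with uncentred use the visit contrasts describe change at zero use. Repeating with sessions per week covers the frequency part of the hypothesis.

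Before the windows are fixed, two sections must be reconciled: Methods asks for use over 6 months, while Treatment phase places the intervention in the first three months.

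The cost is protocol wording, a few lines of code and a few more estimates to report. Questionnaires are already collected at all three times, and Server Data says the accessible data may include the time and duration of each session. A single-visit change contrast is less precise than the level coefficient when within-woman correlation is below about 0.36. Neither the change contrast nor baseline adjustment is unbiased under every baseline link, which is why both are shown.
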